9.9.4.2. Illustration of Discount Function Scenarios

The Figure below shows how the discount function operates with hypothetical data sets

The panels in this figure can be interpreted as follows:

- **Top panel:** The prospective (current) data is very similar to the prior. The discount function allows for full strength of the prior. The posterior (final estimate) is a balance between the prior and prospective study.
- **Middle panel:** The prospective (current) data is similar to the prior. The discount function penalty is moderate, resulting in a prior effective sample size of 17 out of a max of 50. Because the agreement is reasonable, the posterior (final estimate) is similar to both the prior and prospective study.
- **Bottom panel:** The prospective (current) data shows lower performance than the prior. The discount function produces a substantial penalty resulting in no weight to the prior. The posterior (final estimate) is essentially the same as the prospective (current) estimate.

9.9.4.3. Simulation of Primary Efficacy Endpoint Operating Characteristics

Simulations were performed to assess operating characteristics for the primary efficacy endpoint and are presented in the two tables below. We used 8000 trial simulations to estimate the power and 15000 simulations to estimate the type I error. The overall power for the primary efficacy endpoint from **Table 4** is 96%, with a one-sided type I error rate of 0.038.

Table 3: Simulation Parameters for Primary Efficacy Endpoint

Prior Baseline Adjusted RDN Group Mean (SE)	-8.85 (1.75) mmHg
Prior RDN Group N	36
Prior Baseline Adjusted Control Group Mean (SE)	-1.80 (1.75) mmHg
Prior Control Group N	36

Maximum Prior Patients	36 + 36 = 72 (out of 80)
Prospective Study Expected Treatment Difference	-5.0 mmHg
Prospective Study RDN Group Mean (SD)	-6.8 (12) mmHg
Prospective Study Control Group Mean (SD)	-1.8 (12) mmHg
Weibull Discount Function Parameters	Shape: $k = 3$, Scale: $\lambda = 0.25$
Attrition rate at 6-months	15%

Table 4: Study Operating Characteristics for Primary Efficacy Endpoint

Trial Success Rate (Power)	96%
Type I Error	0.038
First Interim Look N	N=110 evaluable (~130 randomized)
Power at First Interim Look	83%
Second Interim Look N	N=149 evaluable (~175 randomized)
Power at Second Interim Look	91%
Maximum Study Size	N=221 evaluable (260 randomized)
% of Simulations that Stop for Futility	1.71%

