The prior data consists of the first consecutively randomized 80 subjects in the SPYRAL HTN-ON MED study, which were randomized in a 1:1 ratio to RDN or control. The results from these 80 subjects have already been analyzed and published [6].

The prospective data consists of the following two cohorts:

[figure not shown]
1. Subjects 81 to 106 which have already been enrolled and were randomized in a 1:1 ratio to RDN vs. control, and whose data has not been unblinded and analyzed by Medtronic.
2. All remaining subjects in the SPYRAL HTN-ON MED Study from 107 onwards which will be randomized in a 2:1 ratio to RDN vs control.

The weight of the prior data will be adjusted using a discount function, which scales from 0 to 1, according to the similarity of the prior and prospective data. The discount function adjusts the amount of weight the prior receives. This prevents the use of an informative prior where exchangeability issues are present (e.g., the prior and prospective data are quite different). This discount function approach was proposed by the Medical Device Innovative Consortium (MDIC) working group and is a collaborative

effort between FDA and industry through the MDIC [1,2]. If the analyses show a high level of agreement for prospective data compared to the prior, the prior will be weighted at or near 100%. If the prospective data perform much worse than or much better than the prior, then the prior will receive very little or zero weight. The Bayesian adaptive design is set up to enroll patients until a sufficient sample size is achieved to have high probability of meeting the endpoint.

The sample size of the study will vary from a minimum of 110 to 221 subjects with evaluable data due to the adaptive nature of the trial. This will require approximately 130 to 260 randomized subjects assuming a 15% rate of attrition at 6-months.

- The first interim analysis will take place when we have a minimum of 110 subjects with evaluable data. With an expected attrition rate of 15%, this will require approximately 130 randomized subjects. If the attrition rate is higher than 15%, then additional subjects will be randomized in order to reach a minimum of 110 evaluable subjects.

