- The second interim analysis will take place when we have a minimum of 149 subjects with evaluable data. With an expected attrition rate of 15%, this will require 175 randomized subjects. If the attrition rate is higher than 15%, then additional subjects will be randomized in order to reach a minimum of 149 evaluable subjects.
- If the study does not stop at the first or second interim analyses, then the final look will take place when 260 subjects have been randomized. This will result in 221 evaluable subjects based on a 15% attrition rate.

Simulations of trial design operating characteristics performed to demonstrate control of type I error and power are presented in section 9.9.4.3 for the primary efficacy endpoint.

9. Statistical Methods

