9.9.3. Primary Efficacy Endpoint

The primary efficacy endpoint of the study is the baseline adjusted (ANCOVA) change in SBP from baseline (SV2) to 6-months post-procedure as measured by 24-hour ABPM.

In the context of an ANCOVA linear regression model, $\mu = \mu_t - \mu_c$ represents the baseline-adjusted treatment effect of BP change comparing RDN and control groups where μ_t and μ_c are the baseline adjusted BP changes in the RDN and control groups respectively. Let $\mathbf{y} = \{\mathbf{y}_t, \mathbf{y}_c\}$ and $\mathbf{y}_0 = \{\mathbf{y}_{0t}, \mathbf{y}_{0c}\}$ represent the prospective data and prior data respectively, where $t = \text{RDN group}$ and $c = \text{control group}$. Let the hypotheses for the study be the following:

$$H_0: \mu = 0$$

$$H_a: \mu < 0$$

We reject H_0 if the probability is greater than 97.5%, i.e.

$$P(\mu < 0 | \mathbf{y}, \mathbf{y}_0, \hat{\varrho}(\mathbf{y}, \mathbf{y}_0, \lambda, k)) > 0.975$$

where the notation $\hat{\varrho}(\mathbf{y}, \mathbf{y}_0, \lambda, k)$ is used to denote that the estimate of ϱ depends on the prospective data, prior data, and the Weibull shape and scale parameters. In conjunction with a pre-specified decision rule controlling the prior data weight, the estimate of $\hat{\varrho}(\mathbf{y}, \mathbf{y}_0, \lambda, k)$ represents a measure of similarity between prospective and prior data. Alternatively, in the absence of $\hat{\varrho}(\mathbf{y}, \mathbf{y}_0, \lambda, k)$, i.e., $P(\mu < 0 | \mathbf{y}, \mathbf{y}_0)$, full weight would be given to the prior data.

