9.9.4.1. Discount Function Estimation Method

The power prior discount function method is comprised of four steps: **Compare, Discount, Combine, and Estimate.**

Compare:

We start by stochastically comparing prospective data vs prior data as follows,

For each treatment group, we separately fit the model to the combined prior and pivotal data:

$$y_i = \beta_0 + \beta_1 I(i \in \text{prior}) + \beta_2 x_i + \varepsilon_i, \quad \varepsilon_i \sim N(0, \tau^2),$$

where $I(i \in \text{prior}) = 1$ if the subject is from the prior dataset, and 0 otherwise, y_i is the BP change for the i th observation and x_i is the mean centered baseline BP for the i th observation. With flat priors on

each parameter, we estimate the posterior probability that $\beta_1 > 0$ by first computing, using Monte Carlo sampling

$$p^* = P[\tilde{\beta}_1 > 0 \mid \mathbf{y}, \mathbf{y}_0].$$

Having calculated this separately for both the RDN (p_t^*) and control groups (p_c^*), they are transformed to p_t and p_c using

$$p = \begin{cases} 2p^*, & p^* \leq 0.5 \\ 2(1 - p^*), & p^* > 0.5 \end{cases}$$

Now, under this transformation, if p_t or p_c are close to 0, there is a high probability that the prospective data and prior data come from different populations and discounting should be applied to reduce the influence of the prior. On the other hand, if p_t or p_c are close to 1, there is a high probability that the prospective data and prior data come from similar populations and minimal discounting should be applied.

Discount:

[figure not shown]
We discount α_{max} based on the value of p_t and p_c from the **Compare** step and the discount function $F(p)$,

$$\hat{\alpha} = \alpha_{max}F(p),$$

where $F(p)$ is a function between 0 and 1. A two-sided Weibull function will be utilized as follows:

$$F(p) = 1 - e^{-\lambda p^k}$$

For this study, we will be using a shape parameter of $k = 3$ and a scale parameter of $\lambda = 0.25$ (illustrated below). Note that we will use the same Weibull function parameters for both RDN group and control group, but p_t and p_c will have different values from the **Compare** step.

Combine:

Using the power prior method and $\hat{\theta}$ we can combine the prior and prospective data together using Bayesian techniques to construct the posterior distribution for μ as follows. We first begin with a hierarchical linear regression model of the form:

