9.9.5.1. Bayesian ANCOVA Model with Single Treatment Effect Parameter using Discount Prior Approach

Using the classical ANCOVA parameterization

$$y_i = \beta_0 + \mu I(i \in t) + \beta_x x_i + \varepsilon_i, \quad \varepsilon_i \sim N(0, \sigma^2),$$

there is a single treatment effect, μ . Similar to the power prior methodology, we can determine an informative prior distribution for μ using the feasibility data. The model above is fitted to the feasibility data assuming flat prior distributions, and the marginal posterior distribution of μ extracted. A stochastic comparison is performed in the same manner as Section 9.9.4.1, whereby we pool the feasibility and expansion data (this time pooling over treatment arms as well) and fitting the model

$$y_i = \beta_0 + \beta_1(i \in \text{prior}) + \beta_x x_i + \varepsilon_i, \quad \varepsilon_i \sim N(0, \sigma^2)$$

The same Weibull discounting function is applied as per the primary analysis (Section 9.9.4.1) to yield a discounting parameter. The Bayesian ANCOVA model is fitted to the expansion data using flat prior distributions for all parameters except μ , which has a distribution of

$$\mu | Y_0 \sim N(\hat{\mu}, \hat{\sigma}^2 / \alpha)$$

Where $\hat{\mu}$ and $\hat{\sigma}^2$ are the posterior mean and standard error estimates from fitting the ANCOVA model to the feasibility data, and α is the discount parameter. Note that this model is invariant to mean centering of the baseline BP, and therefore we do not apply it.

9.9.5.2. Bayesian ANCOVA Model with Single Treatment Effect Parameter using Full Coefficient Vector Prior Distribution

This analysis uses the same ANCOVA model as 9.9.5.1. with separate priors applied to $\beta = (\beta_0, \mu, \beta_x)'$. The power parameter is then used to down-weight the influence of $\hat{\beta}$, the prior estimate. Note that we consider σ^2 to be a nuisance parameter, and therefore a non informative prior distribution is used in the pivotal data update step. This approach allows for the full covariance matrix of β to be downweighted. In the case of the linear regression normal model $Y = X'\beta + \epsilon$, $\epsilon \sim N(0, \sigma^2)$ with known σ^2 (estimated using the feasibility data), with $D_0 = \{(x_{0i}, y_{0i}); i = 1, 2, \dots, n_0\}$ and starting with a uniform initial prior $\pi_0(\beta) \propto 1$ the power-prior for β simply reduces to

$$\pi(\beta|D_0, \alpha) = N((X_0'X_0)^{-1}X_0'Y_0, \frac{(X_0'X_0)^{-1}\sigma^2}{\alpha})$$

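### One type I error value (0.038) does not show control: under the discount weight that reproduces Table 4, the error averages about 0.07 and peaks near 0.25

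*SAP*

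**What the plan says.** Section 8 states: "Simulations of trial design operating characteristics performed to demonstrate control of type I error and power are presented in section 9.9.4.3". Section 9.9.4.3 then gives 96% power "with a one-sided type I error rate of 0.038", the latter from 15,000 simulations. Table 4 adds cumulative power of 83% and 91% at the two interim looks and 1.71% for "of Simulations that Stop for Futility".

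Table 3 lists the alternative only (prospective RDN -6.8, control -1.8, SD 12). No arm means are given for the null. Section 9.9.3 defines the null as a difference of zero and rejects it "if the probability is greater than 97.5" percent.

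On borrowing, section 9.9.4.1 computes a separate weight for each arm from a Weibull-type function: "For this study, we will be using a shape parameter of $k = 3$ and a scale parameter of" 0.25. The function appears there as 1-exp(-lambda p^k). Section 8 says that when prior and prospective data agree, "the prior will be weighted at or near 100" percent. Section 9.9.4.2 says of its best-agreement example: "The discount function allows for full strength of the prior".

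**The concern.** With arm-wise borrowing, the type I error is a function of the change c that both arms share under the null. If c sits at the prior control mean, the RDN prior conflicts with the data, is discounted away and does no harm. If c lies between the two prior means, neither conflict is strong. Both priors then keep some weight, and both pull the contrast towards -8.85 - (-1.80) = -7.05 mmHg although the true effect is zero. A single value at an unnamed c cannot show control over this range.

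This is the confirmatory efficacy test, and a reader of Table 4 will take 0.038 as its error rate. All five sensitivity analyses in section 9.9.5 borrow from the same 80 subjects, so none shows what the Bayesian test yields on the prospective data alone.

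**Working it through.** **Inputs.** From Table 3: prior means -8.85 and -1.80, each with SE 1.75 and n = 36; prospective SD 12. From Table 4: looks at 110, 149 and 221 evaluable, taken as prospective subjects. From section 8: subjects 81 to 106 at 1:1 (26 x 0.85 = about 22 evaluable), the rest at 2:1. This gives RDN/control sizes of 70/40, 96/53 and 144/77. Success is a posterior probability above 0.975 at any look. Futility at looks 1 and 2 is predictive success below 5%.

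**Method.** Each trial was simulated at summary level.
- Per arm, p is the two-sided tail probability for prospective versus prior mean.
- The weight a is F(p).
- The arm posterior has precision n/s^2 + a/1.75^2.
- The contrast is then tested.

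There were 60,000 trials per point and 200,000 for averages. Two forms of F were tried, plus zero weight.

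**Reproducing Table 4.**

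| Weight | Power by look | Futility stops |
|---|---|---|
| Table 4 | 83 / 91 / 96% | 1.71% |
| 1-exp(-(p/0.25)^3) | 83.4 / 91.5 / 96.5% | 1.5% |
| 1-exp(-0.25 p^3), as shown in 9.9.4.1 | 58 / 74 / 87% | 4.8% |
| zero | 55 / 71 / 86% | 5.2% |

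Only the first form, in which 0.25 acts as a Weibull scale, matches. The form shown has a maximum at p = 1 of 1 - exp(-0.25) = 0.22, which also conflicts with the statements in sections 8 and 9.9.4.2 about weight near 100% and full strength.

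**Type I error under the matching weight, futility applied.**

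| Shared change c (mmHg) | Type I error |
|---|---|
| +2 | 0.049 |
| 0 | 0.041 |
| -1 | 0.037 |
| -1.8 | 0.041 |
| -2.3 | 0.051 |
| -3 | 0.077 |
| -3.55 | 0.113 |
| -5 | 0.228 |
| -5.75 | 0.246 |
| -7 | 0.180 |
| -8.85 | 0.066 |
| -9.5 | 0.049 |
| -12 | 0.045 |

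The simulation SE of the reported value is sqrt(0.038 x 0.962 / 15,000) = 0.0016. So 0.038 is compatible with c from about 0 to -1.8 (0.037 to 0.041), but not with c between about -2.3 and -9.5.

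**Why it rises.** At c = -1.8 the mean first-look weights are 0.00 (RDN) and 0.90 (control), and the control prior is centred on the truth, so nothing is shifted. At c = -5.5 they are 0.40 and 0.41. As an illustration at those mean weights:
- Prior precision is 1/1.75^2 = 0.327.
- RDN: the prior's share is 0.40 x 0.327 / (70/144 + 0.40 x 0.327) = 0.21, and the shift is 0.21 x (-8.85 + 5.5) = about -0.7.
- Control: the share is 0.41 x 0.327 / (40/144 + 0.41 x 0.327) = 0.33, and the shift is 0.33 x (-1.80 + 5.5) = about +1.2.
- The contrast moves by about -1.9 mmHg against a posterior SD of sqrt(1/0.617 + 1/0.412) = 2.0, so by nearly one posterior SD.

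**Average.** Over c ~ N(-1.80, 1.75^2) the error is 0.070. About 39% of that distribution lies between -2.3 and -9.5, 25% below -3 and 16% below -3.55.

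**Comparators.** With zero weights the error is 0.046 to 0.049 at every c tried, so the excess comes from borrowing and not from the three looks. With the formula as shown it is 0.047 at c = -1.8, averages 0.048 and peaks at about 0.054 to 0.058.

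**Robustness.** Normal instead of t criteria gave 0.043 at -1.8, 0.114 at -3.55, a peak of 0.243 and an average of 0.070. Dropping the futility stop from that version gave 0.044, 0.117, 0.248 and 0.073.

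**The case against.** The strongest reply is that 0.038 is probably right where it was computed. Table 3 has -1.8 for control in both the prior and the prospective data, so the natural null puts both arms there, and 0.041 is within about two simulation SEs of 0.038. That is fair: the value is not shown to be false, and the null can be inferred. It is still an inference, and one point is not control.

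The one-SE statement is directional. One SE the other way (-0.05) gives about 0.04. The peak is (5.75 - 1.80)/1.75 = 2.26 prior SEs out, with about 1% of the distribution beyond it. This stands, and it makes the average of 0.070 the more representative figure.

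The large values depend on a weight that is not the formula shown, which may be a typographical or text-extraction error. This also stands. But the formula shown does not deliver the stated power, so no reading tested supports both 96% power and control at every c.

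The SAP sets no ceiling on the error, and dependence on the shared change is inherent in arm-wise borrowing. True; 0.05 is used here only as a reference level. The objection is to the claim of control, not to borrowing.

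Section 9.9.6 plans a frequentist ANCOVA without a prior. It uses the populations of section 9.1.3, defined as all randomized subjects, and does not say that the first 80 are left out. The gap is narrower than a missing class of analysis, but it remains.

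**Conclusion.** The concern holds and should be corrected before the operating characteristics are relied on. Under the only weight tested that matches Table 4, the type I error is about 0.04 near c = -1.8, doubles by -3, triples by -3.55, peaks at about 0.25 and averages 0.070. The claim in section 8 therefore holds only near the favourable null.

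The figures assume SD 12 as the residual SD, no simulated individual baseline covariate, 15% attrition, and the prior fixed at its Table 3 values. Third decimals and the limits -2.3 and -9.5 should not be over-read; the pattern does not depend on them. How likely each c is cannot be settled from the SAP.

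**What to change.** 1. In section 9.9.4.3 and Table 4, state the shared change behind 0.038. Report the type I error, with futility stopping applied, over a grid (for example +2 to -12 mmHg), with its maximum and its average over the prior control mean (-1.80, SE 1.75).
2. In section 8, replace the claim of demonstrated control with wording that refers to this grid.
3. In section 9.9.4.1, check the discount function against the code, print the one in use and reconcile it with Table 4 and with the statements in sections 8 and 9.9.4.2. Section 9.9.5.1 inherits it ("The same Weibull discounting function is applied as per the primary analysis").
4. In section 9.9.5, add the same Bayesian model on prospective subjects only, with both weights set to 0.

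The cost is SAP wording, one simulation rerun and one extra model fit, with no added patients and no change to the decision rule. The downside is a less favourable stated error: a maximum of about 0.25 and an average of about 0.07 if the matching weight is the one in use.

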9.9.5. Primary Efficacy Endpoint Sensitivity Analyses

The following sensitivity analyses will be performed for the primary efficacy endpoint to evaluate the consistence of the results. For each of these analyses we will report the posterior distribution mean of μ , the 95% BCI of μ , and the posterior probability of $\mu < 0$.

9.9.5.1. Bayesian ANCOVA Model with Single Treatment Effect Parameter using Discount Prior Approach

Using the classical ANCOVA parameterization

$$y_i = \beta_0 + \mu I(i \in t) + \beta_x x_i + \varepsilon_i, \quad \varepsilon_i \sim N(0, \sigma^2),$$

there is a single treatment effect, μ . Similar to the power prior methodology, we can determine an informative prior distribution for μ using the feasibility data. The model above is fitted to the feasibility data assuming flat prior distributions, and the marginal posterior distribution of μ extracted. A stochastic comparison is performed in the same manner as Section 9.9.4.1, whereby we pool the feasibility and expansion data (this time pooling over treatment arms as well) and fitting the model

$$y_i = \beta_0 + \beta_1(i \in \text{prior}) + \beta_x x_i + \varepsilon_i, \quad \varepsilon_i \sim N(0, \sigma^2)$$

The same Weibull discounting function is applied as per the primary analysis (Section 9.9.4.1) to yield a discounting parameter. The Bayesian ANCOVA model is fitted to the expansion data using flat prior distributions for all parameters except μ , which has a distribution of

$$\mu | Y_0 \sim N(\hat{\mu}, \hat{\sigma}^2 / \alpha)$$

Where $\hat{\mu}$ and $\hat{\sigma}^2$ are the posterior mean and standard error estimates from fitting the ANCOVA model to the feasibility data, and α is the discount parameter. Note that this model is invariant to mean centering of the baseline BP, and therefore we do not apply it.

9.9.5.2. Bayesian ANCOVA Model with Single Treatment Effect Parameter using Full Coefficient Vector Prior Distribution

This analysis uses the same ANCOVA model as 9.9.5.1. with separate priors applied to $\beta = (\beta_0, \mu, \beta_x)'$. The power parameter is then used to down-weight the influence of $\hat{\beta}$, the prior estimate. Note that we consider σ^2 to be a nuisance parameter, and therefore a non informative prior distribution is used in the pivotal data update step. This approach allows for the full covariance matrix of β to be downweighted. In the case of the linear regression normal model $Y = X'\beta + \epsilon$, $\epsilon \sim N(0, \sigma^2)$ with known σ^2 (estimated using the feasibility data), with $D_0 = \{(x_{0i}, y_{0i}); i = 1, 2, \dots, n_0\}$ and starting with a uniform initial prior $\pi_0(\beta) \propto 1$ the power-prior for β simply reduces to

$$\pi(\beta|D_0, \alpha) = N((X_0'X_0)^{-1}X_0'Y_0, \frac{(X_0'X_0)^{-1}\sigma^2}{\alpha})$$

9.9.5.3. Bayesian ANCOVA Model with Single Treatment Effect Parameter using Propensity Score Overlap

This model will use a propensity score overlap for discounting the overall treatment effect. Similar to the approaches proposed by (Wang et al. 2019, 2020; Chen et al. 2020) [9]-[11], here we explore the propensity score overlap between the feasibility and expansion cohorts. We will fit a propensity score model including baseline covariates for age, gender, body mass index, obstructive sleep apnea, history of type II diabetes, baseline eGFR, baseline 24-hour SBP, baseline 24-hour DBP, medication-compliance at baseline (determined via drug testing), and number of AH medications at baseline. We calculate the proportion overlap of the propensity score kernel density distributions between the feasibility and expansion cohorts (using the Overlapping R package: Pastore M et al [13]). We then run the Bayesian model in 9.9.5.1 using the overlap proportion (between 0 and 1, with 1 = complete overlap and 0 = no overlap) as the discount parameter.

9.9.5.4. Commensurate Prior Model with Beta Priors on the Alpha-Discount Parameters without Mean Centering of Baseline Covariates

The commensurate-power-prior approach (Hobbs et al., 2011 [12]) will be used instead of using the discount-function approach. The following prior and likelihood specifications will be used:

Using a vector notation for the classical ANCOVA parameterization in section 9.9.5.1,

- $Y_0 \sim N(X\beta_0, \sigma_0^2)$, $Y \sim N(X\beta, \sigma^2)$, where, $\beta = (\beta_0, \mu, \beta_x)'$ and similarly for β_0 and X is the design matrix. For simplicity, assume σ_0^2 known - take estimate s_0^2 from D_0 .

- Priors:

$$\begin{aligned} \pi(\beta_0) &\propto \frac{1}{\sigma^2} \\ \pi(\beta_x) &= \text{Normal}\left(\beta_0, \frac{\sigma^2}{\tau}\right) \\ \pi(\sigma^2) &\propto \frac{1}{\sigma^2} \\ \pi(\alpha) &= \text{Beta}(\max(\log\tau, 1), 1) \\ \pi(\log\tau) &= \text{Cauchy}(0, 30). \end{aligned}$$

- τ is the commensurability measure parameter for which a $\text{Cauchy}(0, 30)$ prior is assumed on the log-scale. Thus, the prior on τ is concentrated very close to 0. For $\log\tau \leq 1$, $\alpha \sim \text{Uniform}(0, 1)$ and as τ decreases the prior for β gets flatter. While, as τ increase, the distribution of α tends to get heavier towards 1.
- Mean centering will not be applied to the baseline covariates

